8.2.6. Injection Site Examination

A local reaction is normal after BCG. Site of injection examinations will be performed from Day 8 through Month 6 to evaluate the observed local reactions. As stated in the BCG SSI vaccine package insert (South Africa):

- A small tender red swelling appears at the site of the injection which gradually changes to a small vesicle. An ulcer may appear 2 to 4 weeks after vaccination. An adherent dressing is not recommended.
- The reaction usually subsides within two to five months and in practically all children leaves a superficial scar 2 10 mm in diameter.
- Transient enlargement of the regional lymph nodes (< 1 cm) is normal.
- Enlargement of axillary lymph nodes may be seen less frequently in the months following immunisation. Suppurative lymphadenitis may occur less frequently. This is a benign condition which heals spontaneously, although often only slowly.

The presence and maximum diameter of injection site reactions will be recorded as follows:

- Redness, swelling, or inducation ≤ 20 mm is considered as anticipated.
- Redness, swelling, or induration >20 mm is reported as an AE.
- Papule, vesicle, pustule, ulcer, or scar ≤ 5 mm is considered as anticipated.
- Papule, vesicle, pustule, ulcer, or scar >5 mm is reported as an AE.

The presence and maximum diameter of homolateral axillary lymph nodes larger than 1 cm will be recorded.

8.2.7. Participant Follow-Up

Participants will be instructed to contact a study team member to report new or worsening AEs, as well as new diagnoses, and to come to the study clinic if medical attention is needed.

For emergencies and other unscheduled visits to a medical facility other than the study clinic, medical records will, to the extent possible, be obtained by the investigator.

For participants who attend school, study visits will be scheduled outside of school hours whenever possible. Participants will be asked about the occurrence of AEs and SAEs, concomitant prescription medications/vaccinations, and change in general health status and any other change in status that may affect the participant's participation, as indicated in the SoA.

An HIV blood sample will be collected for HIV testing at screening and again yearly, with preand post-test HIV counseling. HIV counseling will be performed by study staff. In addition, any participant suspected of having TB disease (see Section 8.3.6) will be tested for HIV at the time of diagnosis or as soon as possible following suspicion of TB disease.

All deviations from protocol procedures, evaluations, and/or visits will be documented.

8.3. Adverse Events and Serious Adverse Events

The definitions of AEs, SAEs, serious ADRs, SUSARs, and adverse events of special interest (AESIs) can be found in Appendix 2, Section 10.2.1, and 10.2.2, 10.2.3, 10.2.4, respectively.

AEs will be reported by the participant (or, as appropriate, the participant's legally authorized representative). Biochemistry and/or hematology findings may also qualify as AEs if the investigator considers them as such.

SAEs that the investigator assessed as related to vaccination will be collected throughout the study.

Study nurses and physicians are responsible for collecting and documenting information and events that would potentially meet the definition of an AE. However only the investigator (study physician) is responsible for assessment, including assignment of causality and intensity, reporting and management of all AEs. The investigator is responsible for following up AEs that are serious, considered related to the study intervention or study procedures, or that caused the participant to discontinue the study (Section 7).

8.3.1. Time Period and Frequency for Collecting AE and SAE Information

Type of Event	Collection Time Period
All solicited AEs	Day 1 through Day 7 (inclusive)
Unsolicited AEs	Screening through Day 28 (inclusive)*
All SAEs and AESIs	Screening through Month 6*
Serious ADRs	Day 1 through the end of the study

*Refer to the SoA, Section 1.3 for collection of AEs from time of signed consent.

Distribution and collection days for diary cards are shown in the SoA (Section 1.3).

Medical conditions that begin before the start of study intervention but after obtaining informed consent will be recorded on the Medical History/Current Medical Conditions section of the CRF, not the AE section.

All SAEs and AESIs will be reported to the sponsor or designee within 24 hours, as indicated in Appendix 2, Section 10.2.6. The investigator will submit any updated SAE data to the sponsor or designees within 24 hours of it being available.

Investigators are not obligated to actively seek AEs or SAEs after conclusion of study participation. However, if the investigator learns of any SAE, including a death, at any time after a participant has been discharged from the study, and he/she considers the event to be related to the study intervention or study participation, the investigator must notify the sponsor or designee within the same 24 hours timeline.

8.3.2. Method of Detecting AEs and SAEs

The methods of recording and follow-up of AEs and SAEs are provided in detail in Appendix 2, Section 10.2.5, which includes assessments of intensity, causality, expectedness and outcome of AEs and SAE.

Care will be taken not to introduce bias when detecting AEs and/or SAEs. Open-ended and non-leading questions are the preferred method to inquire about AE occurrences.

8.3.3. Follow-up of AEs

After the initial AE/SAE report, the investigator is required to proactively follow each participant at subsequent visits/contacts. All SAEs will be followed until resolution, stabilization, or the participant is lost to follow-up (as defined in Section 7.3). Refer to Appendix 2, Section 10.2.5.

8.3.3.1. AE Intensity

AEs will be classified by the investigator as mild (Grade 1, not interfering with normal daily activities), moderate (Grade 2, interfering with normal daily activities), severe (Grade 3, preventing normal daily activities) or potentially life-threatening (Grade 4). Refer to Appendix 2, Section 10.2.5.1 and Appendix 5 for details. Note that a body temperature between 37.5°C and 37.9°C, can be captured as an AE, at the PI's discretion.

8.3.3.2. AE Causality

All AEs will be evaluated by the PI or medically qualified designee (ie, investigator, study physician) to assess the relationship between study intervention and AE. Careful medical judgement should be exercised to determine the level of causal relationship between an AE and the study intervention. The causality will be assessed as related or not related.

The sponsor or designee will have the opportunity to confirm the seriousness and case causality based on the clinical judgement of the Medical Monitor and sponsor designee. If a serious adverse event is considered unrelated by the investigator but the sponsor believes that there is a reasonable possibility that the event is related, the sponsor will upgrade the case to a 'related' status. The sponsor or designee will never downgrade a case from serious to non-serious, or related to not related.

Refer to Appendix 2, Section 10.2.5.2 for details. Expectedness of AEs is defined in Appendix 2, Section 10.2.5.3.

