7.1.1. Pausing Rules for Study

Any of the below conditions, if identified either by an investigator, the sponsor or the IDMC, will trigger a pause of the enrollment and pause of administration of study intervention until the IDMC has reviewed the safety data and made a recommendation on how to proceed:

- 1. Anaphylaxis with or without bronchospasm within 4 hours of injection, indicative of an immediate hypersensitivity reaction to the study injection
- 2. 1% of the safety population and at least two participants experience an SAE judged as related to BCG vaccination by the investigator
- 3. 20% of participants and at least ten participants experience a Grade 3 or higher event related to BCG vaccination, as judged by the investigator, with the exception of expected local BCG reactions or local injection site reactions that decrease to < Grade 3 within 48 hours.

If an investigator observes that pausing rule 1 or 2 is met, the investigator will inform the sponsor or delegate as soon as possible and within 24 hours of the observation. The sponsor or delegate will notify all study investigators and the IDMC members of the pause in enrollment as soon as possible and within 24 hours of receiving notification of the condition being met. The IDMC members will review all relevant safety data, convene an urgent ad hoc review meeting and make a recommendation to the sponsor with regards to maintaining the pause in enrollment or resuming enrollment.

If, during one of its scheduled or ad-hoc meetings, the IDMC observes that a pausing rule is met, the IDMC Chair or delegate will inform the sponsor as soon as possible and within 24 hours of the identification of the condition being met. If the IDMC has sufficient information to recommend that enrollment resume, this can be communicated to the sponsor at the same time. The sponsor or delegate will notify all study investigators of the pause in enrollment as soon as possible and within 24 hours of receiving notification from the IDMC.

If the sponsor or delegate observes that a pausing is met, the sponsor will notify all study investigators and the IDMC members of the pause in enrollment as soon as possible and within

24 hours. The IDMC members will review all relevant safety data, convene an urgent ad hoc review meeting and make a recommendation to the sponsor with regards to lifting or maintaining the pause in enrollment.

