7.4. COVID-19 Contingency Plans

7.4.1. Rationale and Plan

The Coronavirus Disease 2019 (COVID-19) pandemic has impacted the world since the beginning of 2020, severely affecting people and societies around the globe.

This study was paused for enrollment by the sponsor, effective 19 March 2020, in order to support social distancing and to help health care professionals address COVID-19.

At the time of the enrollment pause, 349 participants had received investigational product (BCG or placebo) and were on-study.

The Government of South Africa declared a National Disaster on 15 March 2020 and ordered a first lockdown (stay-at-home order) on 26 March 2020. Under the lockdown, most trial participants are not able to come to the investigational site for protocol-specified visits. The sponsor and investigators therefore needed to change study procedures and agreed on telephone contacts as an alternative to study visits for safety assessments, for the duration of the Government restrictions, and/or risks that prevent in-person study visits, as judged by the site PI.

In accordance with the SAHPRA Policy on Conduct of Clinical Trials of Health Products during the Current COVID-19 Pandemic, issued 25 March 2020, this protocol amendment reflects the new and modified processes that were put in place in response to COVID-19. This protocol amendment, therefore, accommodates the changes related to the pandemic that needed to take place in order to continue the study in a manner that minimizes any immediate hazards, and also allows for more flexibility to capture study endpoints, and adds an assessment of SARS-CoV-2 infection and COVID-19 disease.

Changes in study visit procedures, missed visits, and participant discontinuations may lead to missing information (e.g., for protocol-specified procedures). We will capture as much information as possible in the case report form and explain the basis of the missing data.

Approaches used to protect trial participants and to manage study conduct during the COVID-19 pandemic, as well as control measures at study sites, will be documented.

Protocol deviations due to the COVID-19 pandemic will be described in the clinical study report (or in a separate study-specific document) including but not limited to the following:

- Contingency measures implemented to manage study conduct during disruption of the study as a result of COVID-19 control measures.

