10.2.3. Definition of Serious ADR and SUSAR

When an adverse event is judged to be serious and related to an investigational product, it is a Serious Adverse Drug Reaction. A serious unexpected suspected adverse drug reaction is referred to as a SUSAR. Refer to Section 10.2.6 for the different reporting requirements.

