10.2.6. SAEs, AESIs, Serious ADRs, and SUSAR Reporting

Reporting to sponsor delegate's (CRO Safety Team) via the Electronic Data Collection Tool

- The primary mechanism for reporting an SAE or AESI by the investigator to the sponsor or delegate will be the electronic data collection tool.
- The site will enter the SAE or AESI data into the electronic system as soon as it is identified.
- All SAEs (related and unrelated) and AESIs are reported to the sponsor and to the CRO Safety team throughout he first six months after study intervention administration.
- Serious ADRs are reported to the sponsor and to the CRO Safety team for the entire study period. Serious ADRs are reported even after the trial is over, if the sponsor, Medical Monitor or PI become aware of them.

- The investigator must not wait to collect additional information to fully document the event before notifying the CRO Safety team of an SAE or AESI. The initial notification should include the following:
 - Protocol number and name and contact number of the investigator
 - Participant ID number (and initials and date of birth, if available)
 - Date participant received study vaccine
 - SAE term and date of event onset
 - Current status of SAE.
- The investigator is responsible for expedited safety report submission to the Sponsor delegate and the Sponsor delegate reports to SAHPRA within specific time periods of being notified of the event. Therefore, it is important that the investigator submit additional information requested as soon as it becomes available.
- All fatal and life-threatening SUSARs are to be reported to SAHPRA with 7 calendar days after first knowledge with a complete report to be submitted within an additional 8 calendar days. Other SUSARs that are not fatal or life threatening need to be reported to SAHPRA no later than 15 calendar days after first knowledge. The sponsor will notify the IDMC of all SUSARs within the same timelines the report is sent to investigators, health authorities, IRB/IEC and other relevant parties. Any follow-up report will be sent with the same timelines.
- If the electronic system is unavailable, the site may use the paper SAE data collection tool (see next section) instead of the EDC, in order to report the event within 24 hours of becoming aware.
- After the study is completed at a given site, the electronic data collection tool, if used, will be taken off-line to prevent the entry of new data or changes to existing data.

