4.2.3 Independent Data Monitoring Committee (IDMC)

An Independent Data Monitoring Committee (IDMC) will be established for the Gates MRI-TBV01-201 study as an independent advisory committee commissioned and charged with the responsibility of evaluating safety data at regular intervals and on an ad hoc basis as necessary, to ensure the rights and safety of the study participants are safeguarded and that potential risks to participants are minimized. The IDMC will also review results from the primary data analysis (after at least 118 sustained *Mtb* infection events occur in the mITT efficacy population) and the secondary analysis (after all participants have 36 months of follow-up).

The independent IDMC will operate according to the IDMC charter. The IDMC structure, participants and other details are provided in the charter.

The IDMC will meet and review blinded and unblinded data as outlined in the IDMC charter. The following outputs will be generated for each IDMC meeting:

- Overall participant status by site, including the number of participants screened, enrolled, completed, and discontinued.
- Critical and major protocol deviations.
- Demographic and key baseline characteristics.
- Study visits entered.
- Overall summary of AEs.
- AEs by System Organ Class (SOC), Preferred Term (PT) and highest grade.
- Summary of respiratory adverse events by PT.
- Serious adverse events (SAEs) by SOC and PT.
- Serious adverse drug reactions (ADRs) by SOC and PT.
- Unsolicited AEs by SOC and PT.
- Adverse events of special interest (AESIs) by SOC and PT.
- Diary card data.
- Injection area and general body symptoms by maximum severity within 7 days after vaccination as solicited on diary card.
- Injection area and general body symptoms on each day after vaccination (solicited on diary card).
- Summary of injection site examination by visit.

- Summary of screening hematology and chemistry laboratory parameters.
- Pregnancy test results and pregnancy outcomes (by participant listings).
- SARS-CoV-2 results by visit and COVID-19 information for participants with suspected COVID-19 (by participant listings)
- QuantiFERON (QFT) Quantitative and Qualitative Results by-participant.
- Overall summary of participants with events contributing to pausing rules.

The pausing rules for the study are included in Protocol Section 7.1.1 and summarized below:

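### Pausing rule 2 counts only SAEs that the investigator judged related, so an SAE that the sponsor upgrades to related does not count towards the automatic pause

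*Protocol*

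**What the plan says.** Protocol Section 8.3.3.2 has the investigator classify each AE as related or not related. The sponsor then reviews serious cases. If the investigator calls an SAE unrelated and the sponsor sees a reasonable possibility of a link, "the sponsor will upgrade the case to a 'related' status". The wording is mandatory and runs one way only, since the sponsor never downgrades. Section 10.1.2 also lets the Medical Monitor, who acts for the sponsor, raise the causality assessment.

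Protocol Section 7.1.1 lists three pausing conditions, any of which, "if identified either by an investigator, the sponsor or the IDMC, will trigger a pause of the enrollment" and of dosing until the IDMC has reviewed the safety data. Rule 2 is met when 1% of the safety population, and no fewer than two participants, "experience an SAE judged as related to BCG vaccination by the investigator". SAP Section 4.2.3 repeats the rule with the same restriction and lists this output for every IDMC meeting: "Overall summary of participants with events contributing to pausing rules".

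Two reporting provisions bear on the same cases. Protocol Section 10.2.3 states: "When an adverse event is judged to be serious and related to an investigational product, it is a Serious Adverse Drug Reaction". It does not say whose judgement is meant. Section 10.2.6 adds: "The sponsor will notify the IDMC of all SUSARs within the same timelines the report is sent to investigators".

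**The concern.** Rule 2 is the numeric trigger that stops dosing for related SAEs. A numeric trigger exists so that a pause does not depend on someone deciding to call one. Here the sponsor must record an SAE as related whenever it sees a reasonable possibility, and it is one of the parties told to watch for the pausing conditions. Yet the condition itself is defined by the investigator's judgement alone. The sponsor's own case status can therefore meet the threshold while the pausing-rule summary shows the rule as not met. A pause in that situation rests on discretion.

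**Working it through.** The plan gives no figure for this point, so there is none to reproduce. The check is a reading of the text followed by simple threshold arithmetic.

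**Text.** Section 7.1.1 names the investigator, the sponsor and the IDMC as parties who may identify that a condition is met. That settles who may detect the condition. It does not settle whose causality call defines it, because rule 2 names the investigator for that. Sections 8.3.3.2 and 10.1.2 allow a case to be raised to related after the investigator has called it unrelated. No section of either document says that such a case enters the rule 2 count.

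**Threshold.** Reading the rule as at least 1% and at least two participants, the number needed at N dosed is T(N) = max(2, 0.01 × N rounded up). The denominator is the safety population, which is everyone randomized and dosed in both arms (Protocol 9.3). The values of N are:

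- 349, from Protocol 7.4.1: "At the time of the enrollment pause, 349 participants had received investigational product (BCG or placebo) and were on-study";
- 1800, the planned total (Protocol Section 4);
- 2150, the maximum (Protocol 7.4.2).

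For the last two I assume that everyone randomized is dosed.

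| N | 0.01 × N | T(N) | One uncounted participant as share of T |
|---|---|---|---|
| 349 | 3.49 | 4 | 1/4 = 25% |
| 1800 | 18 | 18 | 1/18 = 5.6% |
| 2150 | 21.5 | 22 | 1/22 = 4.5% |

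**Example at N = 349.** Suppose three participants have an SAE that the investigator judged related, and a fourth has an SAE that only the sponsor judged related. As written, the count is 3 against a threshold of 4, so there is no automatic pause. If the sponsor's judgement also counted, the count would be 4 of 4 and dosing would pause. The threshold is the same in both cases; only the count changes. The rule counts participants, so an upgraded SAE in someone who already has an investigator-related SAE makes no difference.

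**What else catches an upgraded case.**

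- If it is unexpected against the package insert (10.2.5.3), it is a SUSAR and goes to the IDMC under 10.2.6.
- If it is anaphylaxis within 4 hours of injection, rule 1 applies, and rule 1 does not depend on the investigator's causality call.
- If it is a listed event such as osteomyelitis or osteitis (2.3), it is also an AESI (10.2.4). Through Month 6 all SAEs and AESIs go to the sponsor within 24 hours (8.3.1), and SAP 4.2.3 gives AESIs their own table at each IDMC meeting, beside the SAE and serious ADR tables.

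What remains is a listed SAE that the investigator calls unrelated and the sponsor upgrades, at a moment when the count is just short of the threshold. The documents give no rate of related SAEs or of upgrades, so no probability of a missed trigger can be calculated.

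**The case against.** The strongest defence is that nothing is broken. Causality status in 8.3.3.2 serves regulatory reporting (10.2.5.2 calls it one criterion for that purpose), and tying a pausing rule to the treating physician's judgement is a legitimate pre-specified choice. The uncounted case is also always known to the party that can act. The sponsor made the upgrade, and 7.1.1 leaves the final decision to pause or resume with the sponsor. The Medical Monitor or PI can pause dosing, which brings the IDMC together ad hoc, and the IDMC can request a pause itself (9.4.6). Harm would need a sponsor that upgrades a case and then neither pauses nor consults the IDMC. This is also a single-dose trial, so a pause protects only people not yet dosed. Protocol Version 7 (July 2023) is concerned with the timing of the primary and Month 36 analyses, and SAP 4.1 speaks of the enrollment extension in the past tense. Both suggest that dosing may be over.

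Most of this stands, and it limits the weight of the point. It does not remove it: a sponsor following the plan exactly can still leave the automatic pause untriggered.

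A reader might go further in three ways that the documents do not support.

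- Sections 7.1.1 and 8.3.3.2 might be thought to contradict each other. They do not: they serve different purposes and each can be followed as written.
- The IDMC might be thought not to learn of an upgraded case. The SUSAR route and the SAE, serious ADR and AESI tables point the other way. How quickly a listed case reaches the IDMC may be set in its charter, which is not available, so silence in the protocol and SAP proves nothing.
- Rule 3 might be thought to need the same repair, since it counts a "Grade 3 or higher event related to BCG vaccination, as judged by the investigator". The mandatory upgrade covers serious events only. The rule 3 threshold at N = 349 is 0.20 × 349 = 69.8, so 70, and one case is 1/70 = 1.4% of it. No change to rule 3 is warranted.

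**Conclusion.** The gap is real on the text of both documents. An SAE that only the sponsor judges related is left out of the rule 2 count, and the count falls short by one for each such participant. In relative terms the effect is largest early: one case is a quarter of the threshold at 349 dosed and about 5% of it at full enrollment. The conclusion assumes the literal reading of rule 2 and of the 1% as a minimum. It affects the automatic trigger only. Discretionary pauses, SUSAR notice and AESI reporting make the exposed scenario narrow, and no analysis, sample size or error rate is touched. It matters only while participants are still being dosed, which the documents do not settle. This is a cheap improvement at the lowest severity, not an error in the plan.

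**What to change.** In rule 2 of Protocol 7.1.1 and SAP 4.2.3, add 'or the sponsor' after the reference to the investigator, so that a related judgement by either counts. Compute the pausing-rule summary in SAP 4.2.3 on that combined status. The thresholds stay as they are.

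The cost is a few words in two documents and one status flag behind an existing IDMC output. The threshold may be reached slightly sooner, which would bring an earlier pause and IDMC look. A protocol amendment also needs IRB/IEC approval before it takes effect (10.1.1), in a trial with five or more sites. If dosing is complete, no change is needed in this trial.
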